5.1 Primary Outcome Measures

- Overall postoperative morbidity rates

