8.1.2 Incidence of postoperative complications

The number of all patients treated with surgery as the denominator and the number of the patients with any intraoperative and postoperative complications as the numerator are used to calculate the proportions.

8.1.3 Incidence of overall postoperative complications: The postoperative complication criteria refer to short-term complications after surgery in the postoperative observation project. The time is defined as within 30th after surgery, or the first discharge time if the days of hospital stay more than 30 days.

8.1.4 Incidence of postoperative major complications: The standard for postoperative major complications refers to the short-term complications in the postoperative observation project. according to the Clavien–dindo grade, IIIA level and above for serious complications, and when multiple complications occur simultaneously, the highest ranked complication is the subject.

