9.3.2 Operative parameters (same for both groups)

Completed by the research assistant on the day of the operation. specific projects include:

- (1) Name of responsible surgeons
- (2) Operation time (min)
- (3) Type of operation, digestive tract reconstruction, intraoperative damage and whether the tumor was ruptured during surgery (intact rupture of the capsule)
- (4) Length of incision (cm)
- (5) Conversion to open surgery or not and the reasons for this decision
- (6) Intraoperative estimated blood loss (ml; from skin cutting to stitching, intraoperative blood loss = (postoperative gauze weight, grams - preoperative gauze weight, grams) *1ml/g+ suction fluid, ml)
- (7) Blood transfusion (ml): in this study, the blood transfusion event is defined as transfusion of red cell suspension (ml) or whole blood (ml)
- (8) Tumor location
- (9) Tumor size (maximum tumor diameter, mm)
- (10) Number of lymph nodes dissected in each group and distant metastasis (location)
- (11) Proximal resected margin (mm), distal resected margin (mm), radicality(R0/R1/R2)
- (12) Intraoperative complications (occurring from skin incision to skin closure) including:

surgery-related complications: intraoperative hemorrhage and injury: A. Vascular injury: A vascular injury is defined as a blood vessel with either a blood vessel clamp or a titanium clamp closure and an intra-cavity suture or any other method to control the bleeding. B. Organ damage: maybe including diaphragmatic injury, esophageal injury, duodenal injury, colon injury, small intestine injury, spleen injury (excluding <1/3 spleen ischemia), liver injury, pancreatic injury, gallbladder injury, kidney damage etc.

C. Tumor rupture: tumor envelope Integrity damage

air abdominal-related complications: high-blood carbonate, mediastinal emphysema, subcutaneous emphysema, air embolism, respiratory circulation instability caused by abdominal pressure.

Anesthesia-related complications: Allergic reactions.

(13) Intraoperative death (occurring during the time period from skin cutting to skin stitching completion) regardless of reason.

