9.3.4 Postoperative observation items

Definition of "postoperative day n": One day from 0:00 to up to 24:00. Up to 24:00 on the day of surgery is "postoperative day 0;" the next day from 0:00 to up to 24:00 is "postoperative day 1;" and so on. From the first postoperative day until hospital discharge, the research assistant should timely fill in the following items and specific observation items including:

(1) Pathologic results:

Original lesion tissue typing, Distant metastasis, and parts, NIH Hazard grading, Radical surgery degree (R0/R1/R2), The total number of lymph nodes, the number of lymph nodes in each group, the number of lymph node metastases in each group and the total number of metastases in pathological specimens were obtained

(2) Postoperative complications :

Postoperative complications are divided into and short-term complications after surgery and long-term complications after surgery. Short-term is defined as within 30 days of surgery or the first discharge if the hospital days > 30 days. Long-term is defined as the period from 30 days or more after the operation, or the first discharge (the hospital days after surgery >30 days) to 3 years after the operation.

Severity of complication is graded according to Clavien–dindo complication scoring system,¹⁹

IIIA level and above are serious complication

I: Any deviation from the normal postoperative course without the need for pharmacologic treatment or surgical, endoscopic, and radiologic interventions. Allowed therapeutic regimens are drugs as antiemetics, antipyretics, analgesics, and diuretics, and electrolytes and physiotherapy. This grade also includes wound infections opened at the bedside.

II: Requiring pharmacologic treatment with drugs other than such allowed for grade I complications. Blood transfusions and total parenteral nutrition are also included.

III: Requiring surgical, endoscopic, or radiologic intervention

IIIa: Intervention not under general anesthesia

IIIb: Intervention under general anesthesia

IV : Life-threatening complication (including CNS complications) requiring IC(intermediate care)/ICU(intensive care unit) management

IVa: Single organ dysfunction (including dialysis)

IVb: Multiple organ dysfunction

V: Death as a result of complications

Classification and name of complication	Diagnostic criteria
Abdominal bleeding	Intra-abdominal hemorrhage requires blood transfusion, emergency endoscopy or surgical intervention to eliminate anastomotic bleeding

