Internal hernia	Postoperative CT findings of cystic or cystic and solid mass, and intestinal aggregation, stretching, translocation, abnormal mesenteric movement, and thickening of the blood vessel.
Alkaline reflux esophagitis	1. Endoscopic examination and biopsy of the upper gastrointestinal

	tract showed evidence of inflammation of the mucous membranes and gastrointestinal metaplasia; 2. CT scan and gastrointestinal barium meal examination showed no expansion or obstruction of the input loop.
Incision splitting	Including partial dehiscence of the incision and full-layer dehiscence
Incisional hernia of abdominal wall	The swelling tumor showing in the surgical scar area or abdominal wall swelling when standing or force. CT shows ventral wall continuity interruption and hernia content extravasation
Incision infection	Thickening of the soft tissue at the incision, in or below the incision of gas, exudation, swelling of the incision or pus from the incision extrusion, or secretion culture of pathogenic bacteria.
Lymphatic leakage	A chyle test when abdominal drainage fluid exceeded 300 ml/day for 5 consecutive days after postoperative day 3.
Pneumonia	Complies with one of the following two diagnostic Criteria: 1. Auscultation/percussion voiced + one of the following: fresh sputum or sputum character changes; blood culture (+); bronchoalveolar lavage fluid, anti-pollution sample brush, biopsy specimens cultured pathogenic bacteria. 2. Chest film hints of new or progressive infiltration + one of the following: fresh sputum or sputum character changes, blood culture (+), bronchoalveolar lavage fluid, anti-pollution sample brush, biopsy specimens cultured pathogenic bacteria; isolate virus or detect IgM, IgG (+) of respiratory viral
Acute pancreatitis	Irritability, abdominal pain, anti-jumping pain, fever, leukocyte increase and blood amylase increased occurring and diagnosed by ultrasound or CT within 3 days after surgery.
Acute cholecystitis	Serum bilirubin exceeding 85 μ mol/l and ultrasound examination shows gallbladder enlargement, wall thickness, signal and sound shadow of gallbladder stone, bile internal sediment, gallbladder contraction bad etc.
Pleural effusion/infection	CT scan showed the localized fluid low density area of thoracic cavity, which could accompany with gas, and culture pathogenic bacteria in thoracic endocrine.

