9.4 Follow-Up

9.4.1 Follow-up Period and strategy

Follow-up visits will be completed by special persons for all cases selected in this study .All patients are followed up with 30 days, Recommend patient follow-up every 3 months during the first 2 years and then every 6 months beyond the third year (1、 3、 6、 9、 12、 15、 18、 21、 24、 30 and 36 months after the operation),and record with patients’ consent. This study suggests that the above examinations should be conducted in the patient's primary surgical research center, but does not exclude outer court review. For Outer Court review, It recommended that visiting the hospital as a three-level hospital, and these information will be recorded by the follow-up specialist. The occurrence of tumor recurrence or metastasis and the survival status of all patients are evaluated and recorded according to the results of the various examinations. Patients who refuse to follow the protocol should be recorded as lost to follow-up, and at the end of the study, these cases should be analyzed together with cases lost to follow-up in line with the criteria of this study.

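### The 9.3.4 complication list that supplies the 30-day primary outcome is filled in only from postoperative day 1 to discharge, and no rule brings later events into the count

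*Protocol*

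**What the plan says.** - **Outcome.** Protocol 5.1 names the primary outcome as "Overall postoperative morbidity rates".
- **Window.** Section 8.1.3 refers to the short-term complications among the postoperative observation items, which are in 9.3.4, and sets the period: "The time is defined as within 30th after surgery, or the first discharge time if the days of hospital stay more than 30 days". Section 9.3.4 repeats it: "Short-term is defined as within 30 days of surgery or the first discharge if the hospital days > 30 days".
- **Collection.** The instruction that opens the 9.3.4 list reads "From the first postoperative day until hospital discharge, the research assistant should timely fill in the following items". The same section defines the day of surgery, up to midnight, as postoperative day 0. Section 11.1.1 makes the discharge form due within three days of first discharge.
- **During surgery.** Section 9.3.2 item (12) covers "Intraoperative complications (occurring from skin incision to skin closure) including".
- **After discharge.** Section 9.4.1 follows all patients at 30 days, with a 1-month time point, and says "The occurrence of tumor recurrence or metastasis and the survival status of all patients are evaluated and recorded". Section 9.4.2 lists physical examination, general condition, blood tests and imaging. Section 11.1.1 requires a follow-up form within 7 days of each time point.
- **Adverse events.** Section 12.2 requires complete collection for 30 days from the last treatment day, whatever the cause, graded by Accordion and CTCAE v4.0.

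**The concern.** The endpoint has a 30-day window, but the list that defines its events is closed at discharge. Section 9.3.3.4 makes absence of complications a condition of discharge, so complications after discharge would be mostly new or recurrent and would not already be on the inpatient form. The follow-up sections ask about recurrence, survival, examination and tests. They name neither the 9.3.4 complications nor readmission.

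If staff follow 9.3.4 as written and the analysis uses that list, the reported figure is an in-hospital rate under a 30-day label. In a non-inferiority comparison this is not a conservative error. Missing the same share of events in both arms shrinks any true difference, while the 15-point margin in 3.3 stays fixed.

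**Working it through.** **1. Setting the windows side by side**

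| Period | Covered by the 9.3.2 or 9.3.4 complication lists as worded? | Other route |
|---|---|---|
| Skin incision to skin closure | Yes, 9.3.2 item (12) | – |
| Skin closure to 24:00 on day 0 | Not named in either list | 12.2; possibly the 9.3.4 form completed next day |
| Day 1 to discharge | Yes, 9.3.4 | 12.2 |
| Discharge to day 30 | No | 30-day visit (9.4.1), follow-up form (11.1.1), 12.2 |

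The 8.1.3 window spans the last three rows. The 9.3.4 instruction, read literally, covers only the third. It also conflicts with its own section, which defines short-term complications to 30 days and long-term ones to 3 years; neither can be complete at discharge.

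**2. Do the other routes feed the endpoint?** Section 8.1.3 refers to the 9.3.4 items, not to 12.2. Section 12.2 uses different grading systems and is not tied to the 9.3.4 diagnostic table. Sections 9.4.1 and 9.4.2 do not mention that table. So the routes exist, but no text turns an event found through them into a primary-outcome event.

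**3. The plan's own sample size.** Inputs from 3.3: 15% in both arms, margin 15 points, α = 0.05, power 80%, 68 per group. The normal approximation at one-sided 0.05 gives 2 × 0.15 × 0.85 × (1.645 + 0.842)² / 0.15² = 70.07, so 71. Exact binomial enumeration of the unpooled Z test gives power 0.786 at 67 and 0.800 at 68. The stated 68 is therefore reproduced at one-sided 0.05, and that setting is used below.

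**4. Illustration of equal under-recording.** The protocol gives no share of events arising after discharge, so the missed share m is an assumption. Assume also true rates of 30% and 15%, exactly at the margin, so that any declaration of non-inferiority is an error. The observed rates are p₁ = 0.30(1 − m) and p₂ = 0.15(1 − m). With SE = √{[p₁(1 − p₁) + p₂(1 − p₂)]/68}, the approximate error probability is Φ[(0.15 − (p₁ − p₂))/SE − 1.645].

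| m | p₁, p₂ | Observed difference | SE | Error, approximation | Error, exact |
|---|---|---|---|---|---|
| 0 | 30%, 15% | 15 points | 0.0705 | 5% | 5% |
| 10% | 27%, 13.5% | 13.5 points | 0.0679 | 8% | 8% |
| 20% | 24%, 12% | 12 points | 0.0651 | 12% | 13% |
| 30% | 21%, 10.5% | 10.5 points | 0.0618 | 18% | 20% |

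For m = 20%: (0.15 − 0.12)/0.0651 − 1.645 = −1.184, and Φ(−1.184) = 0.118.

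The direction follows from the arithmetic once a true excess in the robotic arm exists. The size depends entirely on m and on the assumed true rates.

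**The case against.** The strongest reply is that the quoted sentence tells the assistant when to fill in the form and does not limit which events count. Section 9.3.4 itself speaks of 30 days and 3 years, and its table includes late conditions such as bone disease after gastrectomy. All patients are seen at 30 days, a follow-up form is required, and 12.2 asks for complete collection. Findings from review at another hospital are to be recorded by the follow-up specialist. The Grade 3 restriction in 12.2 applies only to items outside the listed surgery-related events. The primary outcome counts any complication, so a different grading system matters less than it would for major complications. The case report form itself is not shown and may already ask for complications at 1 month.

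Much of this stands, and it rules out several stronger readings that a reader might infer:

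- **That post-discharge events have no recording step.** They have three: the visit, the form and 12.2.
- **That events on the evening of surgery are lost.** The same 9.3.4 list takes transfusion volume from the end of surgery, so items on it can cover day 0. This is a wording ambiguity.
- **That the arm going home earlier is favoured.** The protocol does not predict a difference in stay. Both robotic-versus-laparoscopic total gastrectomy comparisons in its background report no significant difference.
- **That pancreatitis after day 3 cannot be counted.** The criterion does say "occurring and diagnosed by ultrasound or CT within 3 days after surgery", but the table's residual row for other new complications can hold a later case, and the limit may be a deliberate diagnostic definition.

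The objection does not supply the missing link. Even on its reading, no text says that an event found at the 30-day visit or in the adverse-event log is checked against the 9.3.4 criteria and added to the numerator.

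**Conclusion.** The point holds as a misalignment between the collection rule and the primary endpoint. Section 9.3.4 closes the complication list at discharge, the 1-month items do not reopen it, and the routes that do reach day 30 are not connected to the outcome definition. The conclusion rests on the protocol text alone; the case report form could close the gap in practice, but the protocol should state the rule.

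The under-count cannot be sized from the protocol. The error rates in the table rest on assumed missed shares of 10% to 30%, equal in both arms, and on true rates placed at the margin. They show that equal loss is enough to weaken the non-inferiority conclusion, without any difference in stay. The day-0 hours are a lesser matter of wording.

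**What to change.** 1. In 9.3.4, state that postoperative complications are recorded from skin closure to the end of the window defined in 8.1.3.
2. Add the 9.3.4 complication table, with Clavien-Dindo grade, onset date and readmission, to the 1-month items in 9.4.2 and to the existing follow-up form, completed for every operated patient.
3. State that adverse events collected under 12.2 within the window are checked against the 9.3.4 criteria and, where they meet them, counted in the primary outcome.

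The sponsor may also be asked to reconcile the 3-day limit in the acute pancreatitis criterion with the 30-day window.

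The visit and the form already exist, so the cost is a wording amendment and a few more form lines. The recorded complication rate may rise slightly.

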3.2 Case group

Group A (Experimental): Robotic-assisted Total Gastrectomy with D2 Lymphadenectomy

Group B (Compared): Laparoscopic-assisted Total Gastrectomy with D2 Lymphadenectomy

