9.3.1.4 Regulations on the extent of the gastrectomy

Follow the Japanese gastric cancer treatment guidelines 2014 (ver. 4) to perform total gastrectomy under the premise of satisfying the oncological principles.

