9.3.1.7 Regulations Regarding Digestive Tract Reconstruction

The digestive tract reconstruction method is determined by the surgeon according to his/her own experience and the specific intraoperative situation. If instrumental anastomosis is used, the surgeon determines whether manual reinforced stitching of the anastomotic stoma is to be performed; the study protocol does not specify.

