Anastomotic bleeding	The postoperative gastrointestinal decompression tube continued to have fresh red blood outflow; the hemoglobin drops more than 1g/dL
Gastrointestinal anastomotic stoma Fistula	Using gastrointestinal angiography to see contrast agent leak out from the anastomosis, or the blue drainage outflow through tube after oral Methylene blue to eliminate the possibility duodenal stump fistula and

Study protocol

	intestinal fistula
Duodenal Stump Fistula	Using gastrointestinal angiography to see contrast agent leak out from the duodenal stump to eliminate the anastomotic fistula or intestinal fistula
Intestinal fistula	Using gastrointestinal angiography to see the blue drainage outflow through tube after oral Methylene blue to eliminate anastomotic fistula and duodenal stump fistula
Stenosis of Anastomosis	Endoscopic examination with a 9.2-mm endoscopy not passing through the anastomosis to eliminate recurrence of tumors
Input jejunal loop obstruction	Abdominal pain, abdominal distension, vomiting and other symptoms. Abdominal flat to see the right upper abdomen expansion of the intestinal loop, and there is a liquid plane, or a visible input loop jejunum giant expansion by barium meal examination.
Intestinal obstruction after operation	Abdominal X-ray shows a plurality of liquid planes and the phenomenon of intestinal effusion with visible isolated, fixed, swelling of the intestinal loop. Total Abdominal CT showed edema, thickening, adhesion of intestinal wall, accumulation of gas in intestinal cavity, uniform expansion of bowel and intra-abdominal exudation.
Early dumping syndrome	Combined the symptoms of sweating, heat, weakness, dizziness, palpitations, heart swelling feeling, vomiting, abdominal colic or diarrhea with the signs of tachycardia, blood pressure micro-rise, breathing a little faster sign after meal 15-30 minutes, and solid phase radionuclide gastric emptying scanning tips stomach quickly emptying.
Late dumping syndrome	Feeling hungry, flustered, out of sweating 2-3 hours after the meal . Blood sugar is less than 2.9mmol/L, excluding other diseases that cause hypoglycemia
Intestinal ischemia and necrosis	Under the digestive endoscopy, the intestinal mucosa congestion, edema, bruising, mucosal hemorrhage, the mucous membrane being dark red, the vascular network disappearing, can have part mucosal necrosis, following with mucosal shedding, ulcer formation with annular, longitudinal, snake and scattered in the ulcer erosion.

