DIC	1. There are basic diseases easily leading to DIC, 2. There are more than two clinical performances: (1) severe or multiple bleeding tendencies; (2) Microcirculation disorder or shock cannot be explained by the original disease. (3) Extensive skin mucosal embolism, focal ischemic necrosis, shedding and ulcer formation, or unexplained lung, kidney, brain and another organ failure. (4) anticoagulant treatment is effective. 3. The laboratory meets the following conditions: (1) there are 3 or more experimental abnormalities: platelet count, prothrombin time, activated partial coagulation enzyme time, thrombin time, fibrinogen level, D-two poly, and (2) difficult or special cases for special examination.

Other	Complications other than the above complications, which do not exist before surgery but appear after surgery
-------	--

(1) Blood test items (At postoperative day 1, 3, 5)

Peripheral blood routine assessment: Hb, RBC, WBC, LYM, NEU, NEU%, and PLT、 MONO;

Blood biochemistry: Albumin, prealbumin, total bilirubin, AST, ALT, creatinine, urea nitrogen, fasting blood glucose, potassium, sodium, chlorine, calcium, CRP, IL-6, PCT, Blood amylase, ascites amylase.

(2) Postoperative rehabilitation evaluation:

Time to first ambulation (hours), time to first flatus (hour), time to liquid diet, time to removal of gastric tube (d), daily volume of gastric drainage (ml), time to removal of abdominal drainage tube (d), daily volume of drainage (ml).Blood transfusion volume (ml) from the end of surgery to postoperative discharge: a transfusion event is defined as infusion of the red blood cell suspension (ml) or whole blood (ml).Postoperative hospital stays (days): periods form surgery day to first discharge day

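### The early dumping row requires a scan showing rapid emptying of the stomach, which no per-protocol patient can satisfy after total gastrectomy

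*Protocol*

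**What the plan says.** The early dumping row in the table of Protocol Section 9.3.4 lists symptoms and signs 15 to 30 minutes after a meal. It then adds, joined by a plain conjunction and with no alternative route, "solid phase radionuclide gastric emptying scanning tips stomach quickly emptying".

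The operation is the same resection in both groups: "Group A (Experimental): Robotic-assisted Total Gastrectomy with D2 Lymphadenectomy" and "Group B (Compared): Laparoscopic-assisted Total Gastrectomy with D2 Lymphadenectomy" (Section 3.2). Section 9.3.1.4 tells the surgeon "to perform total gastrectomy under the premise of satisfying the oncological principles". Reconstruction is left open: "The digestive tract reconstruction method is determined by the surgeon" (Section 9.3.1.7).

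The table feeds the primary outcome. Section 8.1.3, on overall postoperative complications, states: "The postoperative complication criteria refer to short-term complications after surgery in the postoperative observation project". The window is 30 days after surgery, or first discharge if the stay is longer.

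The table ends with a catch-all row, Other: "Complications other than the above complications, which do not exist before surgery but appear after surgery".

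**The concern.** The row makes a finding about the stomach a necessary condition for a complication in a study whose operation removes the stomach. A patient with typical post-meal symptoms and signs fails the definition, however clear the episode.

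The consequence is a choice that the protocol does not settle. Either the episode is not counted, and the morbidity rate omits it unless the patient has another complication, or someone decides case by case to count it elsewhere. The design is open (Section 3.4) and non-randomised (Section 3), and a research assistant completes the postoperative items (Section 9.3.4), so that decision would be made with the group known. A report of no early dumping could then mean only that it could not be recorded under its own heading.

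**Working it through.** **Plan's own figure.** The only design figure nearby is 68 per group (Section 3.3: 15% in both groups, margin 15 points, power 80%). Exact binomial enumeration of an unpooled Z test at one-sided 0.05 gives power 0.786 at 67 and 0.8003 at 68. Among group sizes 64 to 73, 68 is the first to reach 80%. The one-sided reading is an assumption, because Section 3.3 does not state sidedness. The figure reproduces, and this point does not depend on it.

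**Can the row be met?**
1. The row needs symptoms, signs and a scan showing rapid stomach emptying, all together.
2. Sections 3.2 and 9.3.1.4 require total gastrectomy in both groups.
3. Treatment that violates the protocol is a withdrawal criterion (Section 4.3, item 22), and all analyses are per protocol (Section 10.1). A patient left with a gastric remnant has not had the study operation.
4. So the number of per-protocol patients able to meet every element, read literally, is 0 in each group.

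**Comparison within the table.** The late dumping row rests on symptoms 2 to 3 hours after a meal and a laboratory value: "Blood sugar is less than 2.9mmol/L, excluding other diseases that cause hypoglycemia". That can be met without a stomach, so the problem is specific to the early dumping row.

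**Can the event fall inside the primary window?** Discharge requires satisfactory intake of a soft diet (Section 9.3.3.4), so patients eat within the window and a post-meal event can occur there. How often is not stated.

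**Effect on the comparison.** Let p_R and p_L be the morbidity rates with dumping counted, and d_R and d_L the proportions whose only complication is early dumping.

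- Counted difference = (p_R − d_R) − (p_L − d_L) = (p_R − p_L) − (d_R − d_L).
- If d_R = d_L, the expected difference is unchanged.
- If d_R > d_L, leaving dumping out favours the robotic group; if d_R < d_L, it counts against it. The documents give no reason to expect either.

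**Scale per patient.** This is a unit of arithmetic, not an estimate of incidence.

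- The planned 15% is 0.15 × 68 = 10.2 patients per group.
- Each uncounted patient with no other complication lowers that group's rate by 1/68 = 1.5 points. A patient who also has another complication is counted anyway, so the rate does not change.
- One-sided 95% half-width at 15% in both groups: 1.645 × √(2 × 0.15 × 0.85 / 68) = 10.1 points.
- With one patient removed from each group, the rate is 0.15 − 1/68 = 13.5% and the half-width is 1.645 × √(2 × 0.1353 × 0.8647 / 68) = 9.6 points.

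Equal omission thus lowers both rates and narrows the interval a little, without moving the expected difference.

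**The case against.** The strongest reply is that the event need not be lost. An episode that fails the early dumping criterion is arguably not that listed complication, so the Other row can take it in. Clavien-Dindo grade I also covers any deviation from the normal course. This stands in part. A reader might infer that early dumping is zero by definition in the morbidity rate, and the documents do not support that. Zero holds for the row itself, read literally. Whether the episode reaches the total is ambiguous: the Other row can also be read as closed to anything named above it, and the Clavien-Dindo scale grades severity rather than replacing a row's diagnostic criterion.

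A reader might also treat the scan's absence from the examination schedule as a second defect. It is not one. Section 9.4.2 allows further evaluation at the physician's discretion, and other rows rely on tests outside the routine postoperative items, such as methylene blue or pulmonary angiography.

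A third tempting inference is bias toward no difference and hence toward non-inferiority. The row is identical for both groups, and the reconstruction rule is not group-specific. A shift in the risk difference would need dumping to differ between groups, which nothing in the protocol indicates.

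Finally, removing the scan takes away the row's only objective element in an open study. That is a fair cost, but an objective element that cannot be satisfied offers no protection.

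**Conclusion.** Wrong as written, minor. The early dumping criterion contradicts the operation studied, and this is a stated rule rather than a detail left for the analysis plan. Episodes are either uncounted in the primary outcome or coded at the discretion of unblinded staff.

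The effect is probably small: one row among many, the same in both groups. It can understate both morbidity rates and conceal a difference in this component if one exists. It cannot be sized beyond the per-patient arithmetic, because the documents give no early dumping rate, no share arising within the window and no overlap with other complications.

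The conclusion assumes a literal reading of the row and patients who received the study operation. Under the all-operated denominator in Section 8.1.2, a patient whose stomach was not fully removed could in principle meet the row, but that patient did not have the operation under study. An assessor might also read the scan as transit through the reconstruction, which the protocol does not say.

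**What to change.** Reconcile the early dumping row with total gastrectomy. Remove the stomach-emptying-scan element from the endpoint definition, and count the event on the post-meal symptoms and signs already listed in the row. State which combination of them is required and apply it identically in both groups. This changes how the event is counted for the endpoint; it does not direct how a patient is investigated or treated.

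The cost is one table entry, with no added test or visit. The downside is that the event then rests on clinical signs recorded without blinding, some of them soft, so uneven ascertainment between groups becomes possible and counted morbidity may rise slightly. Fixing the required combination in writing limits the first risk but does not remove it.
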